1. *Describe the criteria that define who will be excluded in the study as a numbered list:*
 1. Patient refusal.
 2. Impaired hearing.
 3. Patient is taking at least one anxiolytic medication daily at baseline.
 4. No anxiety (a score of 0, on a scale of 0-10 of pre-music exposure anxiety) after consent is given.
 5. ASA physical status rating of IV or higher. (Incapacitating disease that is a constant threat to life; a moribund patient who is not expected to live 24 hours with or without surgery)
 6. Severe medical condition(s) of the fetus or other pregnancy complications (ex: congenital heart defects, physical malformations, pre-term delivery, etc.)
2. *Describe in detail how the eligibility criteria will be assessed and satisfied (e.g., medical record review, physical examination):*
A brief medical record review, discussion with the patient, and pre-music anxiety assessment (after consent is given) will be performed.
3. *State who will determine eligibility. Note that those who are designated to determine eligibility must have appropriate training, expertise, and oversight, for example a physician PI or Co-I on a biomedical study:*
Either the PI or Co-investigator will determine final eligibility.
4. *Can study subjects participate in another research study while participating in this research study:*
 Yes No

D.3 Withdrawal of Subjects

1. *Describe anticipated circumstances under which subjects will be withdrawn from the research without their consent:*
Participants who score a 0 on their pre-music anxiety assessment will be withdrawn from the study.
2. *Describe procedures that will be followed when subjects withdraw voluntarily or are withdrawn from the research, including the possibility of partial withdrawal from study intervention with continued data collection:*
Participants who are withdrawn from the study will be provided the standard of care at Tufts Medical Center. All collected data and identifying information will be promptly destroyed.
3. *Describe any necessary safety precautions to be applied to subjects who withdraw or are withdrawn (tapering drug doses, evaluative x-ray, etc.):*
 N/A

D.4 Recruitment and Retention

D.4.1 Local Recruitment Methods

Describe the following attributes of the recruitment plan for the local Tufts site:

1. *When, where, and how potential subjects will be recruited:*
 - a. *Source of subjects (for example, patient population, local community, etc.):*

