6. *For Humanitarian Use Device (HUD) uses provide a description of the device, a summary of how you propose to use the device, including a description of any screening procedures, the HUD procedure, and any patient follow-up visits, tests or procedures* N/A

F.3 Evaluations

Will you perform any laboratory tests for this study?

Yes No

F.4 Collection, Storage, and Use of Human Biospecimens for Unspecified Future Research (formerly referred to as “Tissue Banking”)

Will biospecimens be collected and stored for unspecified future research?

Yes No

G. Ethics and Protection of Human Subjects

G.1 Informed Consent Process

Will subjects be required to provide informed consent?

Yes No

If Yes, respond to all of the following:

1. *Where the consent process will take place (e.g. a private clinic room):*
The informed consent will be taken in-person in the pre-op area in a private room.
2. *Anticipated amount of time a potential subject will have to make a decision about participation in the study:*
The patient is anticipated to decide within roughly 15 minutes. However, this is not a cutoff and it will be ensured that patients will not be coerced and will be given ample time to think about enrollment.
3. *Processes to ensure ongoing consent throughout the study:*
The researcher will be present for the entirety of the study intervention and will be able to stop the intervention at any point if the patient wishes to discontinue their involvement. Patients will also be informed that they are able to withdraw from the study at any time.
4. *Role of each research team member involved in the informed consent process (Please note, in general, for studies designated by the IRB as greater than minimal risk, a physician PI or Co-I must perform the informed consent process with subjects. A study coordinator/clinical research associate may not consent subjects. A study coordinator/clinical research associate may assist with this process; however, the PI or Co-I should be present to discuss the study with the subject and answer questions, and the PI or Co-I should sign the ICF documenting that s/he has performed the informed consent process with the subject and the subject understands the study.):*
Either the PI or Co-I will perform the consent process.
5. *Check to confirm you will follow “[SOP: Informed Consent Process for Research \(HRP-090\)](#)”.*

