For the purposes of this study, the principal investigator will periodically evaluate the safety data and assess the risks and benefits to assess subject safety.
 - c. *How the safety information will be obtained and documented (e.g., case report forms, by telephone calls with participants, printouts of laboratory results, etc.):*
The standard of care at Tufts Medical Center is to collect safety information on all patients undergoing surgery through an established computerized system called Anesthesia Touch. This study will also utilize this system to monitor research safety information.
 - d. *The frequency of data collection, including when safety data collection starts:*
Information will be obtained after subject consent with frequency of data collection aligning with the standard of care at Tufts Medical Center.
 - e. *The frequency or periodicity of review of cumulative data:*
Standard safety data review intervals per Tufts Medical Center protocols.
 - f. *The statistical tests for analyzing the safety data to determine whether harm is occurring:*
The statistical tests that will be performed on the safety data to determine whether harm is occurring will include a chi-squared test, to compare proportions between groups.
 - g. *Any conditions that trigger an immediate suspension of the research or other action for the research:*
In the unlikely event of serious patient harm or an unreasonable level of interference with the standard of care at Tufts Medical Center.

2. *Describe the entity responsible for monitoring the data, and their respective roles (e.g., the investigators, the research sponsor, a coordinating or statistical center, an independent medical monitor, a Data and Safety Monitoring Board (DSMB) /Data Monitoring Committee (DMC), and/or some other entity, and the timeframe for reporting events to this entity:*
As mentioned above, the principal investigator will periodically evaluate the safety data and assess the risks and benefits to assess subject safety.
3. *A copy of the DSMB/DMC Charter if the study is enclosed with the submission:* Yes N/A

G.7 Subject Populations & Vulnerable Populations

1. Can or will pregnant women be enrolled?

Yes No

If Yes, respond to all of the following:

- a. *Describe any preclinical studies, including studies on pregnant animals, and clinical studies, including studies on non-pregnant women, that have been conducted that provide data for assessing potential risks to pregnant women and fetuses:*

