
5. Can or will wards of the state and/or children at risk of becoming wards of the state be enrolled (this includes foster children or any child that is in state custody)?
 Yes No
6. Can or will cognitively impaired adults (adults with impaired-decision making capacity) or adults who may lose the capacity to consent be enrolled?
 Yes No
7. Can or will prisoners be enrolled?
 Yes No
8. Can or will students and/or employees be **targeted** for enrollment in this research?
 Yes No
9. Transgender Subjects: Are you recording sex or gender for your study?
 Yes No

H. Adverse Event Monitoring

H.1 Definitions

Define adverse events (AEs), serious adverse events (SAEs), and unanticipated problems for your study:

N/A, no physical risks are anticipated with this research study, and we will use the definitions in the Tufts Health Sciences IRB's [Reportable New Information policy](#).

H.2 Reporting Procedures

1. *Describe the protocol-specific reporting procedures, including who will be responsible for each step (e.g., PI, Data Coordinating Center, Medical Monitor), which forms should be completed, timeframes for reporting, how reports will be distributed, and what follow-up is required:*

Patients are routinely monitored for development of adverse events as part of their anesthetic care. This occurs on a continuous basis from the moment the anesthetic is administered until the moment the patient is discharged home. Monitoring of patients during the study intervention prior to anesthetic care will be done by the co-investigator, [name], who will coordinate with clinical staff to ensure patient safety. Specifically, the co-investigator will monitor for participant ear injury or agitation. A computerized system exists which alerts clinicians to the development of some adverse effects, which are recorded in the medical record. The co-investigator, will be alerted in these situations and all adverse events will be forwarded to the principal investigator. Clinicians are alerted to events immediately as they occur. Clinical staff are trained to deal with such events. The co-investigator, will be responsible for contacting the principal investigator to report the occurrence of adverse events. The principal investigator will then complete any necessary safety forms, including the Anesthesia Department's Quality Assurance form. The events will be reported within 24 hours to the QI director and the chairman of the department.

H.3 Reportable New Information

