prevented via software functions in the original generation of three-digit numbers. No part of the patient's information or MRN will be used to generate the randomly generated number. Once this unique, randomly generated 3-digit number has been assigned, all coded information will utilize this unique identification number. The 3-digit number will replace the patient's MRN on coded data. The only place where the patient's MRN and their unique 3-digit identification number will coexist is on the physical key that will be kept in the PI's locked office as detailed in section G.3.1. Coded data will be stored with a Tufts CTSI REDCap account. Records will be stored for 7 years after the study is closed with the IRB, per IRB policy. The key will be immediately destroyed once the required number of participants have been recruited and the data compiled.

3. *Describe any procedures that will be used for quality control of collected data:* continual collaboration between PI and Co-I on data collection and handling.

I.5 Randomization

Will subjects be randomized?

Yes No

If Yes respond to all of the following:

1. *Describe the randomization procedures, including the ratio of subjects randomized to each study arm:*
Randomization will be performed to assign study subjects to one of the two intervention groups using “randomizer.org” or a similar online program. This will also assign subjects to a random number to help blind later analysis. Ratio of subjects should be 50/50 in each study arm. Determination of music dosage (the duration of music played for participant listening) will be done using the biased coin up-down sequential allocation algorithm, which is not random.
2. *Describe the blinding procedures:* The PI or Co-I administering the study intervention will be unable to remain blind to the study intervention given the inherent nature of the protocol. This will also be true of the participants, as the intervention treatment arms will likely be easily distinguishable. However, the participants will remain blind to their randomized intervention group until the intervention begins. Given the nature of clinical workflow surrounding cesarean sections, blinding of anxiety level assessment will also not be feasible.

J. Drugs or Devices

1. Will the research involve drugs?

Yes No

2. Will the research involve devices?

Yes No

K. Study Administration

K.1 Setting

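### Section D.3 item 2 destroys withdrawn participants' data with no exception for safety data, so a harm-related withdrawal after music starts would drop out of the planned between-group harm comparison

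*Combined protocol and SAP*

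**What the plan says.** D.3 item 1 gives one anticipated reason for withdrawing someone without her consent: a score of 0 on the pre-music anxiety rating. The prompt at D.3 item 2 is wider. It asks what happens on voluntary withdrawal and on withdrawal by the investigator, "including the possibility of partial withdrawal from study intervention with continued data collection". The answer is standard care, followed by: "All collected data and identifying information will be promptly destroyed." It mentions neither safety data nor continued collection.

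G.1 item 3 lets the researcher stop the session if the participant wants to leave, and adds: "Patients will also be informed that they are able to withdraw from the study at any time."

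G.6 item 1a names agitation and ear or hearing problems as the safety events to collect. Under item 1c they are tracked in the clinical anaesthesia record: "This study will also utilize this system to monitor research safety information." Under item 1f, the tests used to "determine whether harm is occurring will include a chi-squared test, to compare proportions between groups". H.2 adds that "all adverse events will be forwarded to the principal investigator".

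On linkage, I.4 item 2 says the sole location where a patient's "MRN and their unique 3-digit identification number will coexist is on the physical key", and then: "The key will be immediately destroyed once the required number of participants have been recruited and the data compiled."

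**The concern.** The participants most likely to have had one of the two named harms include those who ask to stop and leave because of it. D.3 item 2, taken literally, deletes their study records, while G.6 item 1f plans to judge harm by comparing proportions between the arms. The two sections pull against each other: the harm proportions would be calculated only on those who stayed, and a reported zero could not respond to withdrawals caused by harm.

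This matters because the trial is meant to recommend a listening duration, and B.1 says that dosing should combine an adequate response with little risk of side effects. A woman who could not tolerate her session is direct evidence on that, and a destroyed record cannot be recovered.

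**Working it through.** 1. **Who the rule covers.** The D.3 item 2 prompt names both kinds of withdrawal, and the destruction sentence is its only answer on data. G.1 item 3 allows withdrawal at any time, so withdrawal during music is foreseeable. No other section says what is kept for such a participant. A participant who stops the music but stays in the study is not affected.

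2. **The plan's own figure.** I.2 item 2 enrols up to 33 per arm, expecting about 10% attrition: 33 × (1 − 0.10) = 29.7, or about 30 per arm. This reproduces. In total, 66 − 60 = 6 losses. I.3 item 2 counts everyone who signs consent as enrolled, and the score-0 check comes after consent, so some of the 6 may be score-0 patients who never heard music. The plan gives no reasons for attrition and no harm rate.

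3. **Effect on the overall count.** Let k (0 to 6) be the number who withdraw after music starts because of harm. Assume that the other losses occur before music and that no completer has an event. Retained data then show 0/60 whatever k is. With every starter kept, the proportion is k/(60 + k). Exact (Clopper-Pearson) 95% intervals:

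| k | Retained under D.3 item 2 | All who started music |
|---|---|---|
| 0 | 0/60 (0 to 6.0%) | 0/60 (0 to 6.0%) |
| 1 | 0/60 (0 to 6.0%) | 1/61 = 1.6% (0.0 to 8.8%) |
| 2 | 0/60 (0 to 6.0%) | 2/62 = 3.2% (0.4 to 11.2%) |
| 3 | 0/60 (0 to 6.0%) | 3/63 = 4.8% (1.0 to 13.3%) |
| 6 (bound) | 0/60 (0 to 6.0%) | 6/66 = 9.1% (3.4 to 18.7%) |

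4. **Effect on the between-arm test.** With 30 completers per arm as planned and the assumptions of step 3, the most uneven split is 3/33 against 0/30. The uncorrected Pearson statistic is 63 × (3 × 30 − 30 × 0)² / (33 × 30 × 3 × 60) = 510,300 / 178,200 = 2.86, p = 0.09 (Fisher 0.24). Less uneven splits give larger p-values: 2/32 against 0/30, p = 0.16; 3/33 against 1/31, p = 0.33. So even with every record kept, none of these splits reaches 0.05. The retained data are 0/30 against 0/30, for which the statistic is undefined. Four harms against none (4/33 against 0/33) would give p = 0.039 (Fisher 0.11), but if all four withdrew that arm would have 29 completers, below the plan's minimum.

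5. **Power.** The documents give no event rate. For an assumed 1.1 to 2.9 expected events in total, split evenly or 2:1 between arms of 33, full binomial enumeration gives a chance of p < 0.05 between 0.25% and 5.4% with all records kept. If the event rates are halved to mimic deletion of half the events, the chance is at most 1.0%.

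**The case against.** The strongest reply is that D.3 item 2 is a screen-failure rule. Its answer speaks of participants who are withdrawn, echoing the score-0 case in D.3 item 1, which arises before any music. That reading is plausible and may be what the authors meant. It leaves voluntary withdrawal during music with no rule at all, and the same amendment settles the matter either way.

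A reader might infer that the harm event itself is lost. The documents do not support that: H.2 forwards events to the principal investigator, who completes safety forms, and G.6 item 1c uses the clinical record.

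A reader might also infer from the key rules in I.4 item 2 that the event can never be placed in an arm. That goes too far. The co-investigator gives the intervention unblinded, monitors for these harms and reports them, so a report written at the time could state arm and minutes without the key. What stands is narrower: the plan does not say that these reports do so, or that they feed G.6 item 1f. The data-collection, safety and consent forms are not in the documents and may say more.

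Finally, H.1 anticipates no physical risk, the music comes from a speaker for 1 to 30 minutes with the participant helping to control the volume, and every harm count above is assumed. This limits the importance of the point but does not remove the conflict between the sections.

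**Conclusion.** The point holds in limited form. As written, D.3 item 2 removes a participant who withdraws after music starts from the planned harm comparison by arm, even when harm was the reason. This rests on taking the answer to cover everything its prompt asks about, and on the unseen forms not providing otherwise.

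The size is unknown and probably small. It ranges from nothing (k = 0) to a bound of 0/60 in place of 6/66, under the stated assumptions. The gain from a fix is a complete descriptive harm count, not a better test.

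Two stronger conclusions are not supported. One is that a harm summary by minutes of music is being lost: none is planned, since G.6 item 1f compares groups only and I.1 item 2 lists safety endpoints as not applicable. The other is that the ED95 or the comparison of ED95 between arms is distorted: nothing here shows that. The change should be made because the loss is irreversible and the remedy is nearly free.

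**What to change.** Amend D.3 item 2 to say: *Data are destroyed only for participants withdrawn before music starts. For those who withdraw after music starts, coded data to that point (arm, minutes assigned and heard, reason for withdrawal, any agitation or ear/hearing event) are kept unless the participant asks for removal; removals are counted by arm.*

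Amend G.6 item 1f to say: *Harm is summarised by arm for all participants who started music.* The chi-squared test can stay as a secondary comparison. A listing of each event with its minutes assigned and heard would be a useful optional addition, though the plan does not now contain one.

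The cost is a few sentences, a check that the data form has fields for minutes heard and reason for withdrawal, and possibly one aligned line in the consent form. No extra patients, visits or staff are needed. The downside is that some who withdraw may prefer removal. The wording respects that, so some selective loss can remain, but it would be counted.
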